- Hold atezolizumab for Grade 3 toxicities and initiate treatment with high-dose corticosteroids (1-2 mg/kg/day prednisone or equivalent). Corticosteroids should be tapered over 1 month to 10 mg/day oral prednisone or equivalent, before atezolizumab can be resumed. If symptoms do not improve within 48 to 72 hours of high-dose corticosteroid use, other immunosuppressants may be offered for some toxicities.
- In general, Grade 4 toxicities warrant permanent discontinuation of atezolizumab treatment, with the exception of endocrinopathies that are controlled by hormone replacement therapy.

- The investigator should consider the benefit-risk balance for a given subject prior to further administration of atezolizumab. Resumption of atezolizumab may be considered in subjects who are deriving benefit and have fully recovered from the immune-related event. The decision to re-challenge subjects with atezolizumab should be based on the investigator's assessment of the benefits and risks and documented by the investigator. The Medical Monitor is available to advise as needed.

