6.6.2.2.3. Immune-Related Colitis or Diarrhea

Immune-related colitis has been associated with the administration of atezolizumab.

Management guidelines for diarrhea or colitis are provided in [Table 16](#).

All events of diarrhea or colitis should be thoroughly evaluated for other more common etiologies. For events of significant duration or magnitude or associated with signs of systemic

inflammation or acute-phase reactants (eg, increased c-reactive protein, platelet count, or bandemia): perform sigmoidoscopy (or colonoscopy, if appropriate) with colonic biopsy, with three to five specimens for standard paraffin block to check for inflammation and lymphocytic infiltrates to confirm colitis diagnosis.

Table 16: Management Guidelines for Immune-Related Diarrhea or Colitis

Severity of Event	Management
Grade 1	
 Continue atezolizumab Initiate symptomatic treatment Endoscopy is recommended if symptoms persist for > 7 days Monitor closely
Grade 2	
 Withhold atezolizumab for up to 12 weeks after event onset ^a Initiate symptomatic treatment If strong clinical suspicion for immune-related colitis, start empiric IV steroids while waiting for definitive diagnosis Subject referral to GI specialist is recommended For recurrent events or events that persist > 5 days, initiate treatment with 1–2 mg/kg/day oral prednisone or equivalent. If the event does not improve within 48 hours after initiating corticosteroids, consider adding an immunosuppressive agent. Resume atezolizumab if event resolves to Grade 1 or better ^{a,b} Permanently discontinue atezolizumab and contact the Sponsor if event does not resolve to Grade 1 or better while withholding atezolizumab ^c
Grade 3	
 Withhold atezolizumab for up to 12 weeks after event onset ^a Refer subject to GI specialist for evaluation and confirmatory biopsy Initiate treatment with 1–2 mg/kg/day IV methylprednisolone or equivalent and convert to 1–2 mg/kg/day oral prednisone or equivalent upon improvement. If event does not improve within 48 hours after initiating corticosteroids, consider adding an immunosuppressive agent. Resume atezolizumab if event resolves to Grade 1 or better ^b Permanently discontinue atezolizumab and contact the Sponsor if event does not resolve to Grade 1 or better while withholding atezolizumab ^c

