6.6.2.2.6. Immune-Related Ocular Events

Treatment-emergent ocular events have been associated with atezolizumab. An ophthalmologist should evaluate visual complaints (eg, uveitis, retinal events). Management guidelines for ocular events are provided in [Table 19](#).

Table 19: Atezolizumab Management Guidance of Immune-Related Ocular Events

Severity of Event	Management of Ocular Event
Grade 1	
Continue atezolizumab.Subject referral to ophthalmologist is strongly recommended.Initiate treatment with topical corticosteroid eye drops and topical immunosuppressive therapy.If symptoms persist, treat as a Grade 2 event.
Grade 2	
Withhold atezolizumab for up to 12 weeks after event onset.^aSubject referral to ophthalmologist is strongly recommended.Initiate treatment with topical corticosteroid eye drops and topical immunosuppressive therapy.Resume atezolizumab if event resolves to Grade 1 or better.^bPermanently discontinue atezolizumab and contact the Sponsor if event does not resolve to Grade 1 or better while withholding atezolizumab.^c
Grade 3 or 4	
Permanently discontinue atezolizumab and contact the Sponsor.^cRefer subject to ophthalmologist.Initiate treatment with 1– 2 mg/kg/day oral prednisone or equivalent.If event resolves to Grade 1 or better, taper corticosteroids over \geq 1 month.

^a Atezolizumab may be withheld for a period of time beyond 12 weeks to allow for corticosteroids to be reduced to \leq 10 mg/day oral prednisone or equivalent. The acceptable length of the extended period of time must be based on an assessment of benefit-risk by the investigator and in alignment with the protocol requirements for duration of treatment and documented by the investigator.

^b If corticosteroids have been initiated, they must be tapered over \geq 1 month to \leq 10 mg/day oral prednisone or equivalent before atezolizumab can be resumed.

^c Resumption of atezolizumab may be considered in subjects who are deriving benefit and have fully recovered from the immune-related event. The decision to rechallenge with atezolizumab should be based on investigator's assessment of benefit-risk, and documented by the investigator. The Medical Monitor is available to advise as needed.

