6.6.2.2.10. Immune-Related Nephritis

Immune-related nephritis has been associated with the administration of atezolizumab. Eligible patients must have adequate renal function. Renal function, including serum creatinine, should be monitored throughout study treatment. Patients with abnormal renal function should be evaluated and treated for other more common etiologies (including prerenal and postrenal causes, and concomitant medications such as non-steroidal anti-inflammatory drugs). Refer the patient to a renal specialist if clinically indicated. A renal biopsy may be required to enable a definitive diagnosis and appropriate treatment.

Atezolizumab should be withheld for moderate (Grade 2) immune-related nephritis and permanently discontinued for severe nephritis (Grade 3 or 4). Refer subjects to a renal specialist and consider renal biopsy and supportive measures as indicated. Corticosteroids and/or additional immunosuppressive agents should be administered as clinically indicated. Refer to the current atezolizumab Investigator's Brochure for further guidance on the management of immune-related nephritis.

Subjects with signs and symptoms of nephritis, in the absence of an identified alternate etiology, should be treated according to the guidelines in [Table 24](#).

Table 24: Management Guidelines for Immune-Related Nephritis

Event	Management
Renal event, Grade 1	
 Continue atezolizumab. Monitor kidney function closely, including creatinine and urine protein, until values resolve to within normal limits or to baseline values.
Renal event, Grade 2	
 Withhold atezolizumab for up to 12 weeks after event onset.^a Refer patient to renal specialist. Initiate treatment with corticosteroids equivalent to 1–2 mg/kg/day oral prednisone. If event resolves to Grade 1 or better, resume atezolizumab.^b If event does not resolve to Grade 1 or better while withholding atezolizumab, permanently discontinue atezolizumab and contact Medical Monitor.^c

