6.6.2.12. Immune-Related Myositis

Myositis has been associated with the administration of atezolizumab. Myositis or inflammatory myopathies are a group of disorders sharing the common feature of inflammatory muscle injury; dermatomyositis and polymyositis are amongst the most common disorders. Initial diagnosis is based on clinical (muscle weakness, muscle pain, skin rash in dermatomyositis), biochemical (serum creatinine-kinase increase), and imaging (electromyography/MRI) features and is confirmed with a muscle biopsy.

Subjects with possible myositis should be referred to a rheumatologist or neurologist. Subjects with possible myositis should be monitored for signs of myocarditis.

Subjects with signs and symptoms of myositis, in the absence of an identified alternate etiology, should be treated according to the guidelines presented in [Table 26](#).

Table 26: Management Guidelines for Immune-Related Myositis

Event	Management
Immune-related myositis, Grade 1	
• Continue atezolizumab• Refer subject to rheumatologist or neurologist• Initiate treatment as per institutional guidelines

Event	Management
Immune-related myositis, Grade 2	
 Withhold atezolizumab for up to 12 weeks after event onset^a and contact Sponsor. Refer subject to rheumatologist or neurologist Initiate treatment as per institutional guidelines Consider treatment with corticosteroid equivalent to 1-2 mg/kg/day IV methylprednisolone and convert to 1-2 mg/kg/day oral prednisone or equivalent upon improvement. If corticosteroids are initiated and event does not improve within 48 hours after initiating corticosteroids, consider adding an immunosuppressive agent If event resolves to Grade 1 or better, resume atezolizumab.^b If event does not resolve to Grade 1 or better while withholding atezolizumab,

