Immune-related myositis, Grade 3	
 Withhold atezolizumab for up to 12 weeks after event onset^a and contact the Sponsor Refer subject to rheumatologist or neurologist Initiate treatment as per institutional guidelines Respiratory support may be required in more severe cases Initiate treatment with corticosteroid equivalent to 1-2 mg/kg/day IV methylprednisolone or higher dose bolus if subject is severely compromised (eg, cardiac or respiratory symptoms, dysphagia, or weakness that severely limits mobility); convert to 1-2 mg/kg/day oral prednisone or equivalent upon improvement. If event does not improve within 48 hours after initiating corticosteroids, consider adding an immunosuppressive agent. If event resolves to Grade 1 or better, resume atezolizumab.^b If event does not resolve to Grade 1 or better while withholding atezolizumab, permanently discontinue atezolizumab and contact the Sponsor. Permanently discontinue atezolizumab and contact Medical Monitor.^c For recurrent events, treat as a Grade 4 event. Permanently discontinue atezolizumab and contact the Sponsor.
Immune-related myositis, Grade 4	
 Permanently discontinue atezolizumab and contact the Sponsor.^c Refer subject to rheumatologist or neurologist Initiate treatment as per institutional guidelines. Respiratory support may be required in more severe cases Initiate treatment with corticosteroid equivalent to 1-2 mg/kg/day IV methylprednisolone or higher dose bolus if subject is severely compromised (eg, cardiac or respiratory symptoms, dysphagia, or weakness that severely limits mobility); convert to 1-2 mg/kg/day oral prednisone or equivalent upon improvement. If event does not improve within 48 hours after initiating corticosteroids, consider adding an immunosuppressive agent. If event resolves to Grade 1 or better, taper corticosteroids over \geq 1 month.

Event	Management
IV, intravenous	
^a Atezolizumab may be withheld for a period of time (ie, > 12 weeks after event onset) to allow for corticosteroids (if initiated) to be reduced to ≤ 10 mg/day oral prednisone or equivalent. The acceptable length of the extended period of time must be based on an assessment of benefit-risk by the Investigator and in alignment with the protocol requirements for duration of treatment and documented by the investigator. The Medical Monitor is available to advise as needed.	

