7.2. Prohibited or Restricted Therapy

The following therapies are prohibited until study treatment has been permanently discontinued:

- Any investigational agent or investigational medical device.
- Therapeutic doses of oral anticoagulants (eg, warfarin or other coumarin-related agents, direct thrombin or direct FXa inhibitors, or antiplatelet agents such as clopidogrel, or chronic use of aspirin above low dose levels for cardioprotection per local applicable guidelines).
- Any nonprotocol systemic anticancer treatment (eg, chemotherapy, immunotherapy, radionuclides, drugs or herbal products used specifically for the treatment of the cancer under investigation).

- Concomitant use of denosumab with atezolizumab is prohibited due to a potential for increased risk of infections.
- Immunosuppressive agents including immunosuppressive doses of systemic corticosteroids with exceptions as stated in [Section 7.1](#).
- Metamizole (dipyrone) because of its potential for causing agranulocytosis.

The following therapies should be avoided until study treatment has been permanently discontinued or until otherwise specified:

- Local anticancer treatment including palliative radiation, ablation, embolization, or surgery with impact on tumor lesions should not be performed until radiographic progression per RECIST 1.1 has been established. If clinically unavoidable the investigator should consult the Sponsor prior to the procedure for safety guidance.
- Erythropoietic stimulating agents (eg, epoetin alfa and darbepoetin alfa) should not be used based on a report of increased risk of tumor recurrence/progression associated with erythropoietin (Wright et al 2007).
- Concomitant medications that are known to prolong the QTc interval should be avoided in subjects until they have permanently discontinued cabozantinib or sorafenib treatment (refer to <http://www.qtdrugs.org> for a list of drugs which have the potential to prolong the QTc interval).
- Live vaccines are prohibited while on study and until 5 months after last atezolizumab dose (eg, intranasal influenza, measles, mumps, rubella, oral polio, Bacillus Calmette-Guérin, yellow fever, varicella, and TY21a typhoid vaccines). The use of inactivated (killed) vaccines for the prevention of infectious disease requires Sponsor approval with the exception of an inactivated influenza vaccine, which can be given without Sponsor approval.

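### The concomitant-therapy rules in Protocol 7.1 and 7.2 bar non-steroid immunosuppressive agents that Protocol 6.6.2.2 offers for steroid-refractory immune-related events while atezolizumab is only held

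*Protocol*

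**What the plan says.** Protocol 7.2 opens with therapies that may not be given until study treatment has ended for good. One entry is "Immunosuppressive agents including immunosuppressive doses of systemic corticosteroids with exceptions as stated in" Section 7.1.

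Protocol 7.1 allows corticosteroids in four settings: by local routes with little systemic absorption; systemically for infusion reactions or irAEs, with a taper before the next atezolizumab dose; as prophylaxis for contrast allergy; and short term for acute conditions. It names no other immunosuppressive agent and does not refer to Section 6.6.2.2.

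The atezolizumab toxicity guidance in Protocol 6.6.2.2 goes further than steroids:

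- General Grade 3 guidance, atezolizumab held: "If symptoms do not improve within 48 to 72 hours of high-dose corticosteroid use, other immunosuppressants may be offered for some toxicities".
- Table 16, diarrhea or colitis, Grade 2 (with a matching line for Grade 3), atezolizumab withheld: "If the event does not improve within 48 hours after initiating corticosteroids, consider adding an immunosuppressive agent".
- Table 26, myositis, Grade 2, atezolizumab withheld: "If corticosteroids are initiated and event does not improve within 48 hours after initiating corticosteroids, consider adding an immunosuppressive agent". Grade 3, also withheld: "If event does not improve within 48 hours after initiating corticosteroids, consider adding an immunosuppressive agent".
- Table 19, ocular events, Grade 1 (atezolizumab continued) and Grade 2 (withheld): "Initiate treatment with topical corticosteroid eye drops and topical immunosuppressive therapy".
- Nephritis text in 6.6.2.2.10, which covers Grade 2 (withheld) as well as Grades 3 and 4 (stopped): "Corticosteroids and/or additional immunosuppressive agents should be administered as clinically indicated".

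**The concern.** The two sets of instructions cannot both be followed as written. A site that applies 7.2 literally may not give an agent that the toxicity guidance offers. A site that uses the offer gives a drug that 7.2 lists as prohibited. Nothing in the protocol says which section governs, and 7.2 sends the reader to 7.1 for exceptions, not to 6.6.2.2.

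The decision falls 48 hours into steroid treatment in Tables 16 and 26, and 48 to 72 hours in the general guidance, when an immune-related event is not responding. Doubt then about whether a drug is allowed is a subject-safety matter. It mainly concerns the combination arm, the only arm assigned atezolizumab.

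**Working it through.** No figure in the plan is at issue, so the check is a reading of the sections against each other.

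**Step 1: scope of the prohibition.** Section 7.2 names immunosuppressive agents as a class and gives immunosuppressive doses of systemic steroids as one member of it. The class is therefore wider than steroids.

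**Step 2: scope of the exceptions.** Every immunosuppressive entry in 7.1 is a corticosteroid. The word cannot be stretched to other agents, because the protocol itself separates the two: exclusion criterion 11.f.ii lists corticosteroids and other immunosuppressive medications side by side, and the general Grade 3 guidance speaks of other immunosuppressants after steroids.

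**Step 3: instructions that name a non-steroid agent, by atezolizumab status.**

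| Place | Atezolizumab | Strength | Instructions | Conflict with 7.2 |
|---|---|---|---|---|
| 6.6.2.2 general, Grade 3 | held | may offer | 1 | clear |
| Table 16, Grades 2 and 3 | withheld | consider | 2 | clear |
| Table 26, Grades 2 and 3 | withheld | consider | 2 | clear |
| Table 19, Grades 1 and 2 | continued / withheld | initiate | 2 | only if 7.2 covers topical agents |
| 6.6.2.2.10 text, Grade 2 | withheld | as clinically indicated | 1 | arguable |

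Clear conflicts: 1 + 2 + 2 = 5 instructions in 3 places. Number covered by an exception in 7.1: 0 of 5.

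**Step 4: rows that permanently stop atezolizumab.** A non-steroid agent also appears in permanent-stop rows of Tables 15, 16, 20, 23, 24, 26, 27 and 28 (eight tables). Table 25 would make nine, but in the available text its immunosuppressive line sits in a pericardial row with no atezolizumab action, so its status depends on assuming a cell merged with the myocarditis row. Protocol 6.6.1 lets a subject stop one component and stay on the other. These rows therefore conflict with 7.2 only if cabozantinib continues.

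**Step 5: which section is incomplete.** SAP 6.4 defines immune-modulating medications by their use in managing immune-related AEs from atezolizumab, and SAP 8.3 tabulates AESIs that led to starting them. The SAP names no non-steroid agent, so this is supporting evidence only. Together with the repeated provision in 6.6.2.2, it points to a gap in 7.1 and not to an error in the toxicity guidance.

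**Step 6: effect on the analyses.** Immunosuppressant use is not a censoring trigger for PFS (SAP 7.1.1.4) or OS (SAP 7.1.2.3).

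**The case against.** The best defence is that a sensible investigator will treat the event-specific guidance as governing. The SAP expects such treatment, both Table 26 withhold rows require contact with the sponsor, and Protocol 1.7 puts subject safety first. Much of this stands, and it lowers the practical risk. It is still not a precedence rule. Elsewhere 7.1 does point to toxicity sections, for bisphosphonates and for thromboembolic complications, but it has no such link here.

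A reader might also infer more than the documents support:

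- *Eight conflicts in five places* (5 + 2 + 1 = 8). The two ocular rows count only if 7.2 reaches topical agents. That 7.1 expressly allows topical steroids suggests it does. Against that, 7.2 speaks of systemic steroid doses, 7.1 turns on systemic absorption, and exclusion 11.f.ii concerns systemic treatment. The question is open. The nephritis sentence can be satisfied by steroids alone, and it is followed by a direction to Table 24, whose Grade 2 row lists only steroids.
- *A mandatory step is forbidden.* All five clear instructions are optional, so a site that obeys 7.2 omits nothing that is required. The only direct instruction is the topical ocular one.
- *Sites will be cited for deviations.* SAP 9 gives receipt of a prohibited medication only as an example code, and the deviation management plan is not among the documents.
- *Infusion reactions and CRS are affected too.* Appendix G names steroids, anti-cytokine therapy and experimental treatments. It calls for no other immunosuppressive agent, and 7.2 does not list anti-cytokine therapy, so no conflict is shown.

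**Conclusion.** The contradiction is real and lies in the text: five permissive instructions in three places, none covered by an exception in 7.1, while atezolizumab is only held. This rests on reading corticosteroids in 7.1 as the protocol uses the word elsewhere, and on there being no precedence rule in the documents. Two ocular instructions join the count if 7.2 is taken to cover topical agents. The nephritis text remains arguable, and the permanent-stop rows matter only when cabozantinib continues.

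The severity is minor. The consequence is unclear site instruction at a safety decision point. The number of subjects affected cannot be estimated, because the documents give no rate of steroid-refractory events. Alpha, power and the efficacy analyses are untouched.

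**What to change.** Add one bullet to Protocol 7.1, so that the existing cross-reference in 7.2 picks it up:

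> Non-steroid immunosuppressive agents (systemic or topical) are allowed for management of irAEs and HLH/MAS per Section 6.6.2.2 and Table 28; resumption of atezolizumab remains subject to the criteria in those sections.

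This covers the five clear instructions, settles the ocular and nephritis questions, and covers the permanent-stop rows. Table 28 is named separately because it sits in Section 6.6.2.4. Infusion reactions, CRS and Appendix G should be left out.

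The sponsor has one clinical decision to make. In the withhold-and-resume rows of Tables 16 and 26, resumption depends on event grade and steroid taper only. Whether the added agent also needs a washout before atezolizumab restarts is not addressed, and the sponsor should decide it.

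The cost is one bullet in a protocol amendment. Protocol 14 requires IRB/EC approval of modifications, apart from changes that remove an immediate hazard or are purely logistical or administrative. Lifting a medication prohibition is not evidently either, so a clarification letter alone would not be enough. Data collection and the SAP need no change.

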7.3. Potential Drug Interactions

7.3.1. Potential Drug Interactions with Cabozantinib

Cytochrome P450: Data from a clinical drug interaction study (Study XL184-008) show that clinically relevant steady-state concentrations of cabozantinib appear to have no marked effect on the area under the plasma concentration-vs-time curve (AUC) of co-administered rosiglitazone, a CYP2C8 substrate. Therefore, cabozantinib is not anticipated to markedly inhibit CYP2C8 in the clinic, and by inference, is not anticipated to markedly inhibit other CYP450 isozymes that have lower [I]/Ki values compared with CYP2C8 (ie, CYP2C9, CYP2C19, CYP2D6, CYP1A2, and CYP3A4). In vitro data indicate that cabozantinib is unlikely to induce CYP enzymes, except for possible induction of CYP1A1 at high cabozantinib concentrations (30 μ M).

Cabozantinib is a CYP3A4 substrate and a weak substrate for CYP2C9 (but not a CYP2D6, CYP2C8, CYP2C19, CYP2B6, or CYP1A2 substrate), based on data from in vitro studies. Results from a clinical pharmacology study, XL184-006, showed that concurrent administration of cabozantinib with the strong CYP3A4 inducer, rifampin, resulted in an approximately 77% reduction in cabozantinib exposure (AUC values) after a single dose of cabozantinib in healthy volunteers. Chronic co-administration of cabozantinib with strong inducers of the CYP3A4 family (eg, phenytoin, carbamazepine, rifampin, rifabutin, rifapentine, phenobarbital, and St. John's Wort) may significantly decrease cabozantinib concentrations. The chronic use of strong CYP3A4 inducers should be avoided. Other drugs that induce CYP3A4 should be used with caution because these drugs have the potential to decrease exposure (ie, AUC) to cabozantinib.

Selection of alternate concomitant medications with no or minimal CYP3A4 enzyme induction potential is recommended.

Results from a clinical pharmacology study, XL184-007, showed that concurrent administration of cabozantinib with the strong CYP3A4 inhibitor, ketoconazole, resulted in a 38% increase in the cabozantinib exposure (AUC values) after a single dose of cabozantinib in healthy volunteers. Co-administration of cabozantinib with strong inhibitors of the CYP3A4 family (eg, boceprevir, conivaptan, posaconazole, ketoconazole, itraconazole, clarithromycin, atazanavir, indinavir, nefazodone, neflifavir, saquinavir, ritonavir, lopinavir, telaprevir, telithromycin, and voriconazole) may increase cabozantinib concentrations. Grapefruit, star fruit and Seville oranges may also increase plasma concentrations of cabozantinib and should be avoided. Strong CYP3A4 inhibitors should be avoided and other drugs that inhibit CYP3A4 should be used with caution because these drugs have the potential to increase exposure (ie, AUC) to cabozantinib. Selection of alternate concomitant medications with no or minimal CYP3A4 enzyme inhibition potential is recommended.

Please refer to the drug interaction tables at the following website for lists of substrates, inducers, and inhibitors of selected CYP450 isozyme pathways:

<http://www.fda.gov/Drugs/DevelopmentApprovalProcess/DevelopmentResources/DrugInteractionsLabeling/ucm080499.htm>.

Protein Binding: Cabozantinib is highly bound ($\geq 99.7\%$) to human plasma proteins. Therefore, highly protein bound drugs should be used with caution with cabozantinib because there is a potential displacement interaction that could increase free concentrations of cabozantinib and/or a co-administered highly protein-bound drug (and a corresponding increase in pharmacologic effect).

Other Interactions: Food may increase exposure levels of cabozantinib by 57%, fasting recommendations should be followed. In vitro data suggest that cabozantinib is unlikely to be a substrate for P-glycoprotein, but it does appear to have the potential to inhibit the P-glycoprotein transport activity. Therefore, cabozantinib may have the potential to increase plasma concentrations of co-administered substrates of P-glycoprotein (eg, fexofenadine, aliskiren, ambrisentan, dabigatran etexilate, digoxin, colchicine, maraviroc, posaconazole, ranolazine, saxagliptin, sitagliptin, talinolol, tolvaptan). In addition, cabozantinib was shown to be a substrate of drug transporter multidrug resistance-associated protein 2 (MRP2) in an in vitro assay. Administration of MRP2 inhibitors may result in increases in cabozantinib plasma concentrations. Therefore, concomitant use of MRP2 inhibitors (eg, cyclosporine, efavirenz, emtricitabine) should be approached with caution. Additional details related to these overall conclusions can be found in the investigator brochure.

Administration of the proton pump inhibitor (PPI) esomeprazole resulted in no clinically-relevant effect on cabozantinib plasma PK in healthy volunteers. Therefore, concomitant use of gastric pH modifying agents (ie, PPIs, H₂ receptor antagonists, and antacids) is not contraindicated in subjects administered cabozantinib.

Additional details regarding potential drug interactions with cabozantinib can be found in the Investigator's Brochure.

